8.4 DESIGN: Briefly describe the study design (e.g., observational, interventional, randomized, placebocontrolled, blinded, cross-over, cross-sectional, longitudinal, pharmacokinetic, etc.):

Design & Procedures

1. Subject recruitment: Participants will be recruited in [name] laboratory at UCSF. We plan to enroll a total of 240 subjects healthy volunteers (age range: 21-65 years) in order to complete 100 for the entire effort (R21 and R33 Phases combined). This corresponds to enrolling 68 subjects in the R21 (34/year) and 172 (58/year) during the R33 phase. This takes into account the expected rate of failure to: have a pupillary response to the fear conditioning paradigm (25%) and CO₂ challenge (50% - relevant for last 10 R21 and all R33 subjects); and to meet other screening criteria (see inclusion and exclusion criteria sections). These subjects will be recruited from the local community using posted flyers.

2. R21/R33 Components: R21 Phase:

First 30 Subjects, following the screening visit, these subjects will undergo 2-3 sessions separated by 1 week in which a promising electrode configuration (three promising configurations will each be tested in a cohort of 10 subjects) will be used with tDCS stimulation at increasing electrical dosage during which pupillometry will be carried out to determine the Anxiety Task (a test of responses to electrical pulses delivered to the fingers) or Auditory Oddball Test (AOT; a test of responses to rare vs common sounds) response. During pupillometry while undergoing tDCS, ECG, EEG, respiratory rate, or galvanic skin conductance measures may be obtained. A maximum of 5 total tDCS dosages and sham will be tested.

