It is important to note that the 4 mA maximum dosage is within recommended safety limits. We evaluated tDCS with: 1) the electrodes placed over the ears (external auditory meatus) and; 2) one electrode at the inion (notch on the back of the head at the top of the neck) and the other just under the chin. Pupillometry was carried out during the auditory oddball tasks (AOT) where two tones are played one more frequently than the other and the rare tones are well-established to lead to a neural response approximately 300 msec after the rare tones are played. We found that treatment was well-tolerated in general. We were able to find at least one electrode configuration and polarity (orientation of anode and cathode) associated with a tolerable stimulus intensity for all subjects that had a statistically significant effect on the pupillary AOT response. In 4/5 subjects there was an electrode configuration where the LC pupil dilation response to the rare stimuli was significantly suppressed by tDCS compared with both immediate pre and immediate post-stimulation testing (see Figure 3 for example). In 1 subject the response to the rare tones was enhanced by stimulation. In two of the subjects the direction of effect (suppression or enhancement) differed for the electrode configurations and polarities tested. These findings suggest that we can modulate LC function with tDCS with a substantial effect size, though the findings further indicate that electric field modeling will be needed to determine optimal treatment electrode placement given that effects appear to vary from person-to-person and that it is not possible to predict effects in a simple way, such that without modeling and iteration, we may be as likely to augment as inhibit LC activity, at least in some individuals. The findings also indicate that the effect size of inhibition is large enough to be statistically significant at the $p<0.05$ level in a single trial in an individual. These findings serve as a key basis for the proposed effort, support the need for work to determine optimal electrode placement before trials of tDCS for acute fear could be carried out, and support the use of the AOT as a target engagement measure.

8.7 * TREATMENT PROTOCOL: Is this a treatment study, i.e. does this study intend to provide treatment to individuals with a medical or psychological condition: (REQUIRED)

Yes No

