3. **Anxiety Task:** Using the eye-tracking system to track pupil changes, the subject may undergo the anxiety task which involves two different epochs: high tone and low tone. Before the anxiety task begins, the level of "annoying buzz" will be determined for the subject by the research team, based on the verbal responses from the subject. First, a low level "buzz" (set at 5V) will be presented through stimulation generated to the index and middle fingers of the subject, using the BIOPAC STM-200 Stimulator (duration of less than 0.5 seconds) by the researchers. The subject will be asked to report on a scale of 0 (not at all annoying) to 10 (extremely annoying), how the stimulus feels. The presentation of the "buzz" will increase in increments of 5-10V (with a maximum of 100V) until the subject reports a level 7 for highly annoying. The purpose of this "annoying buzz" is to be highly annoying, but not to provoke pain. Once this level is set, the anxiety task is initiated during which the subject will be seated in a dark room and instructed to focus on crosshairs displayed on a computer monitor. The anxiety task consists of two block types: (1) high tone and (2) low tone. Two tones of different frequencies (high and low) are played for 5 seconds at a time throughout a trial. Each trial lasts 12 minutes and consists of each tone (high and low) played 20 times (totaling to 40 tones at 5 seconds each). Stimulation will be delivered 50% of the time in association with either the high or low tone in a given trial (subject receives stimulation 10 times per trial). At each study visit (up to 3 visits, scheduled one week apart) for subjects 1-30, the subject will complete 4-6 trials during which tDCS will be administered at gradually increasing electrical doses during 50% of the trials. The other 50% of the trials will be administered without tDCS or with sham tDCS to establish the subject's baseline pupil response to the anxiety task. Subjects will be given a 5 minute break between each trial.

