current state with respect to those feelings from 1 (not at all) to 4 (very much so). It will be administered just before and just after CO₂ administration.

5. **Generalized Anxiety Disorder-7 (GAD-7)**. The 7 item questionnaire may be administered at screening visits to identify anxiety state and trait correlations with pupil physiology.
6. **Beck Anxiety Inventory (BAI)**. This questionnaire may be administered at screening visits to identify anxiety state and trait correlations with pupil physiology.
7. **Adverse Effects (AE) Assessment**. The Systematic Assessment for Treatment Emergent Events (SAFTEE) will be used to monitor AEs. It is reliable and valid and used by [name] in prior studies.

Attach any unpublished instruments in the 'Other Study Documents' section of the Initial Review Submission Packet form after completing the study application. Published instruments should NOT be attached.

8.12 * BIOSPECIMEN COLLECTION: Are you drawing any blood or collecting other biosamples (e.g. tissue, buccal swabs, urine, saliva, hair, etc.): (REQUIRED)

Yes No

8.25 STATISTICAL METHODS: Briefly summarize the methods and types of analyses that will be performed:

All dependent measures will be tested for distribution normality and meeting homogeneity of variance requirements for parametric statistics. Data transformations will be conducted where indicated.

1. Primary Hypotheses.

R21. Testing R21 hypotheses equates to testing if the "Go-No-Go" criteria for proceeding to the R33 are met.

1) Hypothesis 2a: We can identify an electrode configuration for active tDCS that is well-tolerated (5-point Likert scale rating mild discomfort) and significantly suppress the Anxiety Task or Auditory Oddball

Task (AOT) pupil dilation response in 8/10 subjects in the 3rd round of treatment optimization. The Anxiety Task or AOT response will be determined using a repeated measures analysis of variance * (RMANOVA) with condition (common vs rare) as the independent measure and pupil diameter as the dependent repeated measure. If there is a statistically significant difference between the two conditions during treatment it will be assumed that suppression did not occur.

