decrease the "buzz" stimuli to the patient's level of comfort, as they self-report "annoying" but not "painful" level. The patient may stop at any time or have the stimulus reduced at any time. The number of stimulations delivered will be limited to 10 per 12 minute trial (stimulation associated with either the high or low tone). Parts of the task may become boring or repetitive. Efforts will be made to limit the number of trials administered per visit to minimize subject boredom and discomfort, while ensuring that adequate amounts of data are being collected.

Inhalation of 7.5% CO₂. The primary adverse effect of 7.5% CO₂ inhalation is the induction of Acute Fear which is also the reason that it is being carried out in this study. The fear is generally well-tolerated and resolves within roughly 10 minutes of the end of inhalation. A small percentage of subjects report increased sweating, tremor, tension, and tight muscles during or shortly after inhalation which is generally well tolerated. A gradual rise in blood pressure and pulse with a final systolic blood pressure rise of approximately 18 points, diastolic blood pressure rise of approximately 3 points, and heart rate elevation of approximately 8 points occurs with CO₂ gas as compared to when subjects received "air" inhalation. In rare circumstances severe anxiety could be elicited. There is no evidence that repeated inhalations increases the risks of severe anxiety in response to inhalation testing or in the year following the inhalations. Several studies have evaluated the effects of repeated inhalations with 7.5% CO₂ and higher percentages of CO₂ and not found evidence that there is an increase in fear elicited or an increase in adverse effects with repeated exposures (Poma et al., 2005; Verburg et al., 1998). In addition, a group of healthy non-anxious subjects undergoing repeated exposure to 20% CO₂ inhalation (N=155) were followed for up to a year and compared to a group of healthy non-anxious control subjects who breathed room air (N=56) and there was no evidence that the exposures to 20% CO₂ increased the risk for anxiety /panic during the year of follow-up (Prenoveau et al., 2006).

ECG. Skin irritation from the ECG electrode pads or pain when removing the pads is a possible risk.

12.3

MINIMIZING RISKS: Describe the steps you have taken to minimize the risks/discomforts to subjects. Examples include:

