The study structure is such that there will be 4 cohorts of subjects each consisting of 10 subjects. Each of the first 3 cohorts will be stimulated with a different tDCS electrode configuration to determine if we can find one which is tolerable and inhibits locus coeruleus activity (as indicated by inhibition of a pupil dilatory response). After each cohort we will carry out an interim analysis to determine if this was the case (80% had tolerability ratings of 2 or less and there was statistically significant inhibition of the pupillary response to the anxiety task or auditory oddball task). Each of these interim analyses will be reported to the DSMB. If after the 3 cohorts are completed and if none of the 3 tDCS configurations tested meet the success criteria, then the study will cease. If one of the tDCS configurations meets the success criteria then an additional 10 subjects will be run using the successful tDCS configuration and using 7.5% CO2 instead of the anxiety task or auditory oddball test to elicit a pupillary response.

13.3 * DATA AND SAFETY MONITORING BOARD (DSMB): Will a Data and Safety Monitoring Board (DSMB) be established: (REQUIRED)

Yes

No

13.4 DSMB DETAILS: Provide details from the DSMB's charter, including meeting frequency, and affiliations and qualifications of members: If the DSMB has not yet been established, submit these details to us as they become available.

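### Hypothesis 2a tests pupil suppression only within the tDCS trials, so a non-significant rare-versus-common difference in effect counts as suppression and the same-visit no-tDCS/sham trials go unused

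*Combined protocol and SAP*

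**What the plan says.** Section 8.25 (R21, Hypothesis 2a) requires a tolerable configuration that significantly suppresses the pupil response "in 8/10 subjects in the 3rd round of treatment optimization". The analysis is a repeated-measures ANOVA of pupil diameter with one factor, common versus rare. The decision rule is "If there is a statistically significant difference between the two conditions during treatment it will be assumed that suppression did not occur".

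Section 13.2 (interim analysis) requires, after each cohort, that "there was statistically significant inhibition of the pupillary response to the anxiety task or auditory oddball task". It names no test and no comparator. It stops the study only if none of the three configurations succeeds, and goes on to the cross-over if one does.

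Section 8.9 (Anxiety Task) says that at each visit in subjects 1-30 "the subject will complete 4-6 trials during which tDCS will be administered at gradually increasing electrical doses during 50% of the trials". It continues: "The other 50% of the trials will be administered without tDCS or with sham tDCS", in order to establish the subject's baseline response. Section 8.4 sets the number of doses: "A maximum of 5 total tDCS dosages and sham will be tested".

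Section 8.6 reports that in 4 of 5 pilot subjects the response was "significantly suppressed by tDCS compared with both immediate pre and immediate post-stimulation testing". Section 10.3 bases the sample size on that result and describes it as suppression relative to no stimulation.

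**The concern.** The rule in 8.25 is worded as an exclusion: a significant difference rules suppression out. Nothing in 8.25 or 13.2 says what rules it in. With one factor in the model and no tDCS-versus-no-tDCS term, the only way to be called suppressed is to fail to reject. Imprecise data then favour success, and a response that is smaller for any reason during the tDCS trial looks like a tDCS effect. Each added dose gives another chance of a non-significant result.

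The call decides which electrode configuration goes into the 10-subject cross-over. At stake is whether that configuration, and the dose labelled as suppressing in subjects 1-30, inhibits the pupil response at all.

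**Working it through.** **Inputs.** The plan gives no power, error rate or effect size for Hypothesis 2a, so there is no stated figure to reproduce.
- Gate: 8 of 10 subjects (8.25).
- Doses: k up to 5 (8.4).
- No-tDCS/sham trials: half of 4-6, so m = 2 or 3 per visit for the Anxiety Task (8.9). For the AOT only a sham is assured, m = 1 (8.4).
- Entry requires a significant pupil response (10.7), and 25% are expected to fail it (8.4, 10.1).
- Assumed: two-sided alpha 0.05, independent tests across doses, and single-trial power p varied over 0.95, 0.90 and 0.75.

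**Step 1. False calls under the present rule, no tDCS effect.** A dose is called suppressing with probability 1 - p, and a subject is called if any dose is: q = 1 - p^k. The gate is P(X ≥ 8) for X binomial(10, q).

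| p | q, k = 5 | gate, k = 5 | q, k = 3 | gate, k = 3 |
|---|---|---|---|---|
| 0.95 | 1 - 0.95^5 = 0.23 | 0.0002 | 0.14 | < 0.0001 |
| 0.90 | 1 - 0.90^5 = 0.41 | 0.014 | 0.27 | 0.0008 |
| 0.75 | 1 - 0.75^5 = 0.76 | 0.56 | 0.58 | 0.13 |

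**Step 2. Let p vary between subjects.** The 0.75 row needs every subject to have power 0.75. Instead, let the non-centrality be normal with SD 1, 2 or 3, set its mean so that 75% pass screening, and keep only those who pass. Over five doses q = 0.468, 0.272 and 0.185, and the gate is 0.036, 0.0008 and 0.00004.

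**Step 3. Which round counts.** If any of three cohorts may qualify (13.2), the false-pass probability is 1 - (1 - gate)^3: 0.0006 at p = 0.95, 0.04 at p = 0.90, and 0.10 or less in the spread model.

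**Step 4. What follows the gate.** The cross-over compares active with control tDCS (8.25, R21 item 3). Assuming two-sided 5%, its error in the suppression direction is 0.025, so a false Go is at most gate × 0.025. At a gate of 0.036 that is 0.0009, and it cannot exceed 0.025 whatever the gate.

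**Step 5. Power of a direct comparison.** Write d = 1.96 + z_p for the expected single-trial statistic. If tDCS abolishes the response, the interaction against m pooled comparison trials (one-sided 0.025) has power Φ(d/√(1 + 1/m) - 1.96).

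| p | d | m = 1 | m = 2 | m = 3 |
|---|---|---|---|---|
| 0.75 | 2.63 | 0.46 | 0.58 | 0.63 |
| 0.90 | 3.24 | 0.63 | 0.75 | 0.80 |

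Under no effect, at most 1 - 0.975^5 = 0.119 of subjects are called, and 8/10 is then falsely passed with probability 1.4 × 10⁻⁶.

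**Step 6. Reaching 8/10 with a working configuration.** If only one dose abolishes the response, P(X ≥ 8) is 0.21 (p = 0.75) or 0.68 (p = 0.90) with m = 3, and 0.03 or 0.22 with m = 1. If the top two of five doses abolish it in every subject, simulation with baselines shared within a visit gives 0.77-0.98 with m = 2-3, and 0.22-0.64 with m = 1.

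**The case against.** The best defence is that 8.25 never says non-significance means suppression. The aim is significant suppression; 8.6 and 10.3 compare with no stimulation; 8.9 collects baseline trials. On that reading the sentence only adds an exclusion to an evident comparison. This stands as a statement of intent, and that the converse holds is an inference. It does not rescue the rule: the one analysis written down lacks the comparison, and no section supplies a positive criterion.

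The objection to size is stronger, and most of it stands. A reader might infer that an inert configuration passes more often than not, from the 0.56. That needs p = 0.75 in every subject, five tolerated doses where 8.4 gives a maximum, and independence. Subjects are screened for a significant response, and the spread model gives 0.036 or less.

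A reader might also infer large inflation from fading. With an assumed 5% fall per trial and tDCS always second in each pair, p = 0.90 gives 68% of subjects called and a gate of 0.34. Both assumptions are invented. Section 12.2 says only "Parts of the task may become boring or repetitive", which concerns tedium and discomfort, not pupil habituation. Fading is a reason to interleave trials, not a measured bias.

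**Conclusion.** The point holds as a defect in the decision rule: as written, failing to find a difference during tDCS is in effect taken as suppression, and the control trials that would answer the question are left out. For p of 0.90 to 0.95 with five tolerated doses, 23% to 41% of subjects would be falsely called, and the 8/10 gate falsely passed with probability 0.0002 to 0.014. Mislabelled subjects and doses are therefore likelier than a falsely passed gate. All figures rest on an assumed p and on independent tests across doses; fewer doses or more precise pupil data shrink them.

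A reader might infer that the trial could make a false efficacy claim. The documents do not support that: the cross-over's active-versus-control test follows, and the R33 comparison is randomized. The consequence is a cross-over spent on an ineffective configuration. It should be fixed, with medium confidence in its size.

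**What to change.** For the Hypothesis 2a gate and the 13.2 interim analyses in subjects 1-30, replace the decision sentence in 8.25 with:

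*A dose counts as suppressing only if the rare-minus-common response (Anxiety Task: paired-minus-unpaired tone) under tDCS is significantly smaller than in the same subject's same-visit no-tDCS/sham trials (condition × stimulation interaction), with tDCS and no-tDCS/sham trials interleaved.*

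Also state one rule for which round counts: 8.25 says the third, while 13.2 accepts any of three.

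For the Anxiety Task this adds no trials. The cost is power per subject and dose: about 58-63% at p = 0.75 and 75-80% at p = 0.90 with 2-3 comparison trials, and 46% and 63% with one, as for the AOT. The sponsor should therefore confirm before cohort 1, with the DSMB and NIH Program, whether 8/10 remains attainable. No particular lower threshold is proposed. One such as 5/10 would pass a configuration that works in only 30% of subjects with probability 0.21-0.28 (2-3 comparison trials), and that trade-off is theirs to judge.

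The titration stop rule in the cross-over and R33 is outside this change. Subjects whom the lower-powered test misses could be terminated under 8.9, and in R33 that would fall after randomization and on the active arm only.

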Last 10 Subjects. These subjects will take part in a double-blind, controlled, randomized, cross-over study over 3 sessions following their screening visit. At session 1 subjects will undergo electrical dose titration with the tDCS electrode configuration resulting from the 3 rounds of optimization using the same procedure as in the first 30 subjects to determine the lowest well-tolerated dose that suppresses the pupil dilation response to the Anxiety Task or Auditory Oddball Test, except that a maximum of 5 tDCS dosages will be tested at this session. At the second and third sessions (1 week apart) subjects will receive doseoptimized tDCS and the control treatment with order randomized along with 7.5% CO₂ (to evoke an LC response) for 20 minutes. The 7.5% CO₂ will be delivered pre-mixed as provided by Airgas. 7.5% CO₂ is commonly and safely used in the field of study. A mixture of CO₂ 7.5%/O₂ 21%/N 71.5% will be purchased premixed from Airgas and shipped to UCSF. At these sessions, the VAS-A and STA-I will be administered 5 minutes prior to and just after the 20 minute session and VAS-A will also be obtained at 5, 10, 15, and 20 minute points of the CO₂ inhalation. tDCS will be administered during the last 5 minutes of the 20 minute CO₂ inhalation period. Subjects will be monitored for an hour post-session for safety and will undergo study physician assessment to determine suitability to leave. Following the 2nd treatment session participation will end except that subjects will be called the next day to assess for adverse effects and appropriate care will be given if any are found.

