1. **Pupillometry Procedure:** We will employ a Tobii Pro eye tracking system to measure pupil response. Pupil diameter will be recorded continuously from the each eye at a sampling rate of 60 Hz via a sensor bar attached to a computer monitor. We will capture pupil size at baseline, in response to the Anxiety Task or Auditory Oddball Test (AOT), pain-induced conditioned fear test, and administration of 7.5% CO₂. Data will be segmented into epochs from 0 to 12 s relative to the acquisition onset of each stimuli or experimental condition. An average pupil diameter measure will then be calculated for the corresponding volume by taking the mean across the remaining non-artifactual samples in that epoch. During tDCS the pupil diameter will be averaged over 1 minute periods while subjects are staring at a dark screen in a dark room. For 7.5% CO₂ response the pupil diameter will be averaged over 1 minute periods while subjects are staring at a dark screen in a dark room. This will be computed at baseline, and at 5, 10, 15, and 20 minutes after the start of CO₂ inhalation and 5 minutes and 30 minutes post-inhalation. During pupillometry while undergoing tDCS, ECG, EEG, respiratory rate, or galvanic skin conductance measures may be obtained.

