2) Hypothesis 1b: In 10 controls in a cross-over study, 7.5% CO₂ inhalation significantly increases the VAS-A "fearful" rating compared to baseline rating. This will be tested with a RMANOVA where condition (7.5% CO₂ vs air) is the independent variable and VAS-A "fearful" rating is the repeated dependent measure.

3) Hypothesis 2a, 1b, 1a: In a cross-over study, active dose-personalized tDCS significantly suppresses the LC pupil response to 7.5% CO₂. This will be tested by carrying out a RMANOVA where treatment (active tDCS vs control) is the independent variable and mean resting pupil diameter is the repeated dependent measure. This will also establish that 7.5% CO₂ elicits an LC response as measured by mean pupil diameter (Hypothesis 1b) and whether subjects can guess whether they received active tDCS or the control to assess the viability of the control treatment (Hypothesis 1a).

4) Hypothesis 2b: Active tDCS will be safe in terms of there being no adverse effects of more than mild severity and rated to be possibly, probably, or definitely related to treatment.

R33 Testing R33 hypotheses assesses if the criteria for proceeding to further development are met.

1) Hypothesis 3a: Dose-personalized tDCS decreases VAS-A "fearful" rating compared to sham in a parallel-group, randomized, double-blind study. This will be determined by computing the effect size in terms of Cohen's D for the tDCS vs control treatment effect on the VAS-A "fearful" rating at the expected peak CO₂ effect (20 minutes after start of CO₂).

2) Hypothesis 3b: tDCS is safe as indicated by the absence of adverse effects of more than mild severity rated to be possibly, probably, or definitely related to treatment.

Secondary/Exploratory Analyses. Examples of Exploratory/Secondary analyses of interest include: 1) Testing if there are significant differences between active tDCS and the control therapy on the pupillary response to CO₂ in the R33 study; 2) Evaluating tDCS vs control treatment effect sizes for

other VAS-A items and the STAI in the R33 study; 3) mapping the time-course of effects on LC post-tDCS

8.26 REFERENCES: List only the 5-10 most relevant references (a separate bibliography can be attached for reference purposes if this study involves novel approaches, agents, or an emerging technology that the IRB may not be familiar with):

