(50% - relevant for last 10 R21 and all R33 subjects); and to meet other screening criteria (see inclusion and exclusion criteria sections). These subjects will be recruited from the local community using posted flyers.

10.3 SAMPLE SIZE JUSTIFICATION: Explain how and why the number of people was chosen. For multi-site studies, this is referring to the number that will be enrolled across all sites:

Given the nature of the R21/R33, we have few analyses for which consideration of power is relevant. These include the determination of whether there is a statistically significant difference in pupil response to the Anxiety Task or the rare and common stimuli in Auditory Oddball Task (AOT) and determination of whether in the R21 cross-over study active tDCS has a significantly greater effect on the pupil response to CO₂ than sham. For the Auditory Oddball Task (AOT), in our pilot work where we were able to demonstrate differences between rare and common stimuli and the suppressing effects of tDCS (See Preliminary Studies). N=10 subjects in our R21 pilot cross-over study will be sufficient based on our pilot work (C.3.5). We estimate that the size of the effect of a dose-personalized, electrode configuration optimized tDCS vs control therapy will be at least as large as the effect size we observed in our preliminary work with a pilot electrode configuration where we found that in 4/5 subjects we could demonstrate a statistically significant suppression of the AOT pupil response compared with no stimulation which serves as a pilot proxy for the control therapy.

10.4 * PARTICIPANT AGE RANGE: Eligible age ranges: (REQUIRED)

- 0-6 years
- 7-12 years
- 13-17 years
- 18-64 years
- 65+

10.5 * STUDY POPULATIONS: Data will be collected from or about the following types of people (check all that apply): (REQUIRED)

- Inpatients
- Outpatients
- Family members or caregivers
- Providers
- People who have a condition but who are not being seen as patients
- Healthy volunteers
- Students
- Staff of UCSF or affiliated institutions
- None of the above

10.6 * SPECIAL SUBJECT GROUPS: Check the populations that may be enrolled: (REQUIRED)

- Children / Minors
- Subjects unable to consent for themselves
- Subjects unable to consent for themselves (emergency setting)
- Subjects with diminished capacity to consent
- Subjects unable to read, speak or understand English
- Pregnant women
- Fetuses
- Neonates
- Prisoners
- Economically or educationally disadvantaged persons

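### The R21 cross-over pupil test, a Go-No-Go criterion with 10 subjects, does not say which pupil reading it analyses, omits period, and cannot show the CO₂ pupil response it is said to establish

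*Combined protocol and SAP*

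**What the plan says.** Section 8.25 (Statistical Methods, R21, item 3) specifies a repeated measures ANOVA "where treatment (active tDCS vs control) is the independent variable" and "mean resting pupil diameter is the repeated dependent measure". It names no reading or average, no time or treatment-by-time term, no pre-stimulation value, and no period or sequence. The opening of the R21 hypotheses makes these tests the Go-No-Go criteria for the R33. Item 3 adds that the same analysis will establish that CO₂ elicits an LC response in the pupil, and whether subjects can guess their treatment.

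The timing is given elsewhere:

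- Section 8.4 (last 10 subjects): "tDCS will be administered during the last 5 minutes of the 20 minute CO₂ inhalation period". The design is a cross-over over two sessions: "subjects will receive doseoptimized tDCS and the control treatment with order randomized". CO₂ is given at both.
- Section 8.9, item 1, on the pupil under CO₂: "This will be computed at baseline, and at 5, 10, 15, and 20 minutes after the start of CO₂ inhalation". Two later readings follow once the gas has stopped, one after 5 minutes and one after 30. On stimulation: "During tDCS the pupil diameter will be averaged over 1 minute periods while subjects are staring at a dark screen in a dark room".
- Section 8.9, item 8: subjects breathe air through the mask for 10 minutes before CO₂, and baseline measures are taken then.

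By contrast, sections 8.11 and 8.25 fix the R33 fear rating at 20 minutes. Section 10.3 calls 10 subjects sufficient for the cross-over on the strength of pilot work.

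**The concern.** Treatment is the only factor, the outcome is called repeated, and seven pupil readings exist per session. One possible reading of the model is therefore a treatment main effect over the inhalation readings. Three of those four precede any effect of the current, so their active-control difference is pure noise around zero and the average would hide a real effect.

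Because the text is silent, the analyst could also choose among single readings and averages after seeing the data, at the gate to a 60-subject trial.

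Two further gaps sit in the same item. Order is randomised but period is not modelled. And one model is credited with a conclusion about CO₂ that its only contrast does not address.

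**Working it through.** **The plan's own figure.** N = 10 cannot be reproduced. Section 10.3 gives no effect size, SD, alpha or power. Its basis is 4 of 5 pilot subjects with significant suppression of the oddball response, which is not resting pupil diameter under CO₂.

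**Inputs.** From the documents: n = 10; two sessions; inhalation readings at 5, 10, 15 and 20 minutes; current on in minutes 15 to 20. Assumed, because not stated: two-sided alpha 0.05; single-reading SD 1; an effect of 1 SD at 20 minutes only; correlation ρ between readings in the same session; correlation s between readings of the same subject in different sessions (s ≤ ρ).

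**Formulas.** Let D be the active-minus-control difference at one time.

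- Var(D) = 2(1 − s), so the standardised effect at 20 minutes is d20 = 1/√[2(1 − s)].
- For the mean of four readings the effect is 1/4 and the variance is ½[(1 − s) + 3(ρ − s)], so d4 = 0.25/√variance.
- Power is that of a paired t-test: noncentral t with 9 df, noncentrality d√10, critical value 2.262.

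Example, ρ = 0.7 and s = 0.5: d20 = 1/√1 = 1.000. The variance for the mean is ½(0.5 + 0.6) = 0.55, so d4 = 0.25/0.742 = 0.337. Power is 80% against 16%.

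| ρ | s | d20 | power, 20 min only | d4 | power, mean of four | power, 20 min adjusted for 15 min |
|---|---|---|---|---|---|---|
| 0.3 | 0 | 0.707 | 51.4% | 0.256 | 11.3% | 49.5% |
| 0.5 | 0 | 0.707 | 51.4% | 0.224 | 9.7% | 57.7% |
| 0.7 | 0 | 0.707 | 51.4% | 0.201 | 8.8% | 73.4% |
| 0.8 | 0 | 0.707 | 51.4% | 0.192 | 8.5% | 86.2% |
| 0.5 | 0.3 | 0.845 | 66.3% | 0.310 | 14.2% | 63.9% |
| 0.7 | 0.3 | 0.845 | 66.3% | 0.256 | 11.3% | 76.7% |
| 0.7 | 0.5 | 1.000 | 80.3% | 0.337 | 15.9% | 80.9% |
| 0.7 | 0.6 | 1.118 | 88.1% | 0.423 | 22.3% | 85.0% |
| 0.8 | 0.7 | 1.291 | 95.1% | 0.456 | 25.3% | 94.0% |

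The last column is simulated: regression of the 20-minute difference on the 15-minute difference, 8 df. The correlation between those two differences is (ρ − s)/(1 − s), so a stable subject component, which pairing already removes, leaves less for the covariate to explain. A simple 20-minus-15 change score is worse: its standardised effect is d20/√[2(1 − r)], where r is that correlation, so it helps only if r exceeds 0.5. At d20 = 1.0 and r = 0.3 it gives 66% against 80%.

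**Post-inhalation readings.** With d20 = 1.0 and r from 0.9 to 0.3, the mean of all seven readings gives 7 to 10% power. If the effect lasts to 5 minutes after inhalation, it gives 14 to 25%.

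**Period.** Take d20 = 1.0, order split 5:5, and a shift between sessions measured in SDs of D (simulated).

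| shift | power without period term | power with period term | type I error without period term |
|---|---|---|---|
| 0 | 0.80 | 0.79 | 0.051 |
| 0.5 | 0.72 | 0.79 | 0.031 |
| 1.0 | 0.49 | 0.79 | 0.007 |
| 1.5 | 0.20 | 0.79 | 0.001 |

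With balanced order the omission makes the test conservative. Balance is not stated: a 7:3 split would bias the estimate by (7 − 3)/10 = 0.4 of the shift.

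**CO₂ response.** Both arms of the contrast are measured under CO₂, so a CO₂ effect common to the sessions cancels in active minus control. Item 2 of section 8.25 does set CO₂ against air, but only for the fear rating.

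**The case against.** The strongest reply is that item 3 most naturally means one value per session. In items 1 and 2 of section 8.25 the same wording is used, and there the repetition is plainly over the two conditions within a subject. Section 8.9 defines a one-minute pupil mean during stimulation, and the plan treats 20 minutes as the CO₂ peak for the fear rating. On that reading nothing is diluted. This stands: a reader might infer that the plan leaves out the 20-minute reading, or that a false No-Go is likely, but the text supports neither. It is silent, and the power loss is conditional on averaging.

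A reader might also infer that the 15-minute value should be the standard covariate because it buys much power. The documents give no variance components, and the table shows anything from a large gain (51% to 86%) to a small loss (88% to 85%). Nor do they say that the 15-minute mean ends before the current starts; if it overlapped, the covariate could absorb part of the effect.

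On period, the documents report no shift, and without one the omission costs nothing. The responder criterion applied at the first CO₂ session (section 10.7) makes a shift plausible but does not show one.

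Finally, the sentence on establishing the CO₂ response also covers treatment guessing, which no pupil model could test, so it may refer to the cross-over study as a whole. The CO₂ pupil test is then unspecified rather than ruled out, and the readings for it are collected. The stated contrast still cannot supply it.

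**Conclusion.** The point holds as a gap in specification at a Go-No-Go test. The analysed reading is not named, and the choice matters: with 10 subjects and an assumed 1 SD effect confined to 20 minutes, power is about 8.5 to 25% on the mean of the four inhalation readings and 51 to 95% on the 20-minute reading. These ranges rest on the assumed effect, alpha and correlations. The direction does not depend on the particular values tried; the size does. After-effects could reach the post-inhalation readings, but not those at 5 and 10 minutes, nor a 15-minute mean completed before current starts.

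The missing period term is a lesser matter, negligible without a shift and costly with one. That active versus control cannot show a CO₂ pupil response follows from the design and needs no assumption about numbers.

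**What to change.** - State the primary test as active versus control on the one-minute mean pupil diameter at 20 minutes, with that minute defined as falling while current is on, and with subject and period in the model. State alpha, sidedness and whether order is balanced.
- Specify the CO₂ pupil response as a separate within-subject comparison: the on-CO₂ reading taken before current starts against the air-mask baseline.
- If wanted, add adjustment for the same session's 15-minute value as a supporting analysis, by ANCOVA or mixed model rather than a change score, provided that minute is defined as ending before current starts.

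The scheduled readings already cover this, so the change is SAP wording and a precise definition of two measurement minutes. Period takes one degree of freedom (9 to 8; power 0.80 to 0.79 in the case above), and the optional covariate one more.
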